	
 • he is no longer chemically castrated as demonstrated by testosterone levels greater than or equal to 50 ng/dL, • a rise in PSA over baseline of ≥ 0.5 ng/mL is observed, • he has completed 24 weeks of double blind treatment, and elected not to continue into the extension period, or • he has completed 52 weeks of study drug administration. 
At the conclusion of study participation, patients will be advised to resume standard of care treatment under the supervision of their healthcare provider. While on treatment, patients will be evaluated at Day 1 and every 2 weeks, for the first 24 weeks and every 4 weeks thereafter with a final post-treatment follow-up visit 2 weeks (+/- 2 days) post last dose administration.

Number of Patients	Planned sample size is 120 male patients with advanced androgen-sensitive prostate cancer, randomized equally to one of four treatment groups (N=30 per group).
Inclusion Criteria	
 1. Males, Ages 18 and older 2. Body Mass Index (BMI) between 18 and 35 kg/m² (inclusive) 3. Not currently hospitalized 4. Clinical indication of adenocarcinoma of the prostate evidenced by a biopsy report on record 5. At present receiving ADT treatment with 
 a. a GnRH agonist b. for at least 2 months but not longer than 36 months without interruption 
Note: If the patient received GnRH agonist treatment prior to the treatment described under 5a and b, there must be evidence of a period without GnRH agonist treatment for a minimum of 2 months prior to starting the present treatment as is seen, for example with intermittent treatment regimens.
 
 6. Able to initiate Screening procedures 2 weeks prior to the next scheduled injection with a GnRH agonist 7. Willing to discontinue current ADT regimen for the duration of the study 8. T level less than 50 ng/dL at Screening 9. WHO/ECOG performance status of 0 or 1 10. Life expectancy of at least 1 year 11. Adequate renal function demonstrated by not having elevated blood urea nitrogen (BUN) or Creatinine Screening lab values 12. Willing and able to communicate with the Investigator and study staff, and willing and able to complete all phases and all procedures required of the study 13. Provide voluntarily consent to participate in this study and provide written informed consent prior to start of any study-specific procedures

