3.0 Study Design

Patients will participate in a 24 week double-blind treatment period and will be allowed to continue treatment with their assigned study drug for up to 52 weeks as long as they remain chemically castrated. Entry criteria include prostate cancer patients who are currently receiving treatment with a GnRH agonist depot injection for at least 2 months but not longer than 36 months without interruption, and have testosterone levels < 50 ng/dL at Screening. At the scheduled time point for the next GnRH agonist depot injection, patients will be randomized to receive either placebo or low, mid or high dose BHR-200. The study will enroll 120 patients with 30 patients randomized into each of the 4 treatment groups as shown in Table 1.

Table 1 Treatment group allocation for study BHR-200-201

Treatment Group	Number of Patients	Dose	Number of Pump Actuations*	
Placebo	30	10	0 mg estradiol	1 actuation
		10	0 mg estradiol	2 actuations
		10	0 mg estradiol	3 actuations
BHR-200 Low Dose	30	3 mg estradiol	1 actuation	
BHR-200 Mid Dose	30	6 mg estradiol	2 actuations	
BHR-200 High Dose	30	9 mg estradiol	3 actuations	

*1 actuation of the pump dispenses [REDACTED]

Patients will be offered optional low-dose radiation for the prevention of gynecomastia (Hedlund 2000, Widmark et. al. 2003). Timing of the administration of the low-dose radiation will be at the discretion of the Investigator.

Levels of total Testosterone, estradiol, and estrone will be assessed every 2 weeks for all patients through Week 24 and then every 4 weeks through the End of Study Visit at Week 54 (see [Schedule of Assessments in Appendix 1](#)). Patients will remain in the study and administer daily doses of the assigned study drug until they are no longer chemically castrated as indicated by a measurement of T \geq 50 ng/dL after 4 weeks of double-blind treatment, a rise over baseline PSA of > 0.5 ng/mL is observed, or if 52 weeks of study drug administration have been completed. Patients discontinued from the study will be advised to resume standard of care treatment in consultation with their healthcare provider.

Safety assessments will include AEs as well as the measurement of typical blood chemistry, hematology and urinalysis parameters, as well as coagulation factors, hormone assessments, bone biomarkers, and PSA ([Section 6.1](#)).

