4.3 Early Withdrawal of Patients

A patient is free to withdraw from the study at any time for any reason without prejudice to their future medical care by the physician or at the institution. The Investigator or Sponsor may also withdraw the patient at any time in the interest of patient safety. The primary reason for withdrawal must be recorded in the patient's medical record and on the withdrawal form in the Case Report Form (CRF). If a patient is withdrawn for more than one reason, each reason should be documented in the source document and the most medically significant reason should be entered on the CRF. The withdrawal of a patient from the study should be discussed where possible with the Medical Monitor before the patient stops administration of the study drug. If the study drug is discontinued, the final evaluations will be performed as completely as possible. Any comments (spontaneous or elicited) or complaints made by the patient and the reason for termination, date of stopping study drug and the total amount of study drug administered must be recorded in the CRF and source documents.

The following are reasons to terminate the participation of a patient in the study:

- The patient is no longer chemically castrated, after 4 weeks of double-blind treatment or anytime thereafter, indicated by a measurement of T \geq 50 ng/dL. (*treatment failure*)
- The patient's PSA rises >0.5 ng/mL above the baseline measurement (*treatment failure*)
- Lost to follow-up: patient fails to return to the study site for scheduled visits and does not respond to multiple telephone or written attempts to contact (these attempts should be documented).
- Withdrawal of consent: patient decides to stop participation in the study for any reason or is unable to complete the study as described in the study protocol. Although a patient is not obliged to give his/her reason for withdrawing prematurely, the Investigator will make a reasonable effort to obtain the reason while fully respecting the patient's rights. Every effort will be made to contact a patient who fails to attend any follow-up appointments/contacts in order to complete study assessments.
- Administrative: the Sponsor decides to terminate or discontinue the study (either at the study site or the entire study).

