9.1 Adverse Event Collection

AEs will be captured for the duration of the study. The reporting period begins with the first dose of Study Drug (Study Day 1) and ends at Week 54 or the End of Study. For this study, an AE is defined as: “Any unfavorable or unintended sign (including an abnormal laboratory finding), symptom, or disease, whether or not associated with the treatment and study procedures.” This includes any newly occurring event or previous condition that has increased in severity or frequency since the administration of study drug.

AEs may also be reported spontaneously at any time. Details of any adverse or unexpected events, signs, and symptoms will be collected including details of onset, resolution, frequency, severity (as defined below), seriousness, relationship to the drug, effect on the study drug, treatments administered, and outcome. Any AE will be followed, whenever possible, until it returns to the baseline condition or becomes stable with no further change expected.

The safety of BHR’s transdermal estradiol gel has been studied in 25 healthy volunteers using single doses and in 9 patients in the target patient population, men with androgen-positive prostate cancer, using once daily dosing or twice daily dosing for one week. The tolerability of the drug was very good (for full reference, see the Investigator Brochure). In other formulations of transdermal estrogens have been studied in this patient population and the results have been published in peer-reviewed literature. The known side effects of

transdermal estradiol in these study populations, where estradiol was used for up to a year in some cases, include:

- gynecomastia (Bland et al. 2005, Gerber et al. 2000, Ockrim et al. 2003),
- vasomotor symptoms (Hedlund 2000, Spetz et al. 2001),
- loss of libido, and erectile dysfunction (Cox and Crawford 1995, Hedlund 2000, Lycette et al. 2006, Ockrim et al. 2006, Sayed and Taxel 2003)

Particular attention should be paid to the following potential risks previously identified as associated with administration of estradiol in populations of post-menopausal women:

- myocardial infarction
- stroke
- DVT
- pulmonary emboli

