## 4 STUDY OVERVIEW

### 4.1 Study design

This was a multi-center, randomized, double-blind, placebo-controlled, dose-finding study in men with advanced androgen-sensitive prostate cancer. Patients participated in a 24-week double-blind treatment period and were allowed to continue treatment with their assigned study drug for up to 52 weeks as long as they remained chemically castrated. Patients who gave informed consent had screening evaluations, and if fulfilling the entry criteria, were randomized to one of 4 treatment groups: 1mL, 2mL or 3mL of 0.36% BHR-200 (transdermal estradiol gel) or placebo. Study drug was initiated on the day (+/- 5 days) they would be scheduled to receive the next GnRH agonist depot injection. Patients were offered low-dose radiation to aid in the prevention of gynecomastia. Patients applied the study drug once per day. The first dose was applied under the supervision of the

PI/designee. Subsequent doses were self-administered daily by the patient until one of the following occurred:

- he was no longer chemically castrated as demonstrated by testosterone levels greater than or equal to 50 ng/dL,
- a rise in PSA over baseline of  $\geq 0.5$  ng/mL was observed,
- he had completed 24 weeks of double blind treatment, and elected not to continue into the extension period, or
- he had completed 52 weeks of study drug administration.

At the conclusion of study participation, patients were advised to resume standard of care treatment under the supervision of their healthcare provider. While on treatment, patients were evaluated at Day 1, every 2 weeks, for the first 24 weeks, and every 4 weeks thereafter, with a final post-treatment follow-up visit 2 weeks (+/- 2 days) post last dose administration.

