### **12.2 Vital Signs**

Vital sign parameters include systolic and diastolic blood pressure, body weight, height, BMI, respiration rate, temperature, and heart rate. Vital sign values and changes from baseline in these parameters will be presented using descriptive summaries by visit.

A shift from baseline analysis of abnormalities (normal, abnormal/clinically significant, and abnormal/ not clinically significant) will also be presented by counts and percentages at each post-administration visit and in an overall view regardless of post-administration assessment time point. In addition, at each time point, the sums of subjects with normal, abnormal CS, and abnormal NCS values at that time point will be summarized. Also, at each time point the sums of subjects with normal, abnormal CS, and abnormal NCS values at baseline and values at that time point will be summarized.

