## 12.5 Adverse Events

Adverse events (AEs) will be mapped to preferred terms and SOC using the MedDRA coding dictionary.

Summaries of AEs will be also presented based on treatment-emergent AEs (TEAEs), defined as AEs that begin (or if preexisting medical conditions that worsen) after receiving the first application of the study drug. If the adverse event start date is partially or completely missing then the adverse event will be considered treatment-emergent.

The number and percentage of subjects experiencing AEs will be summarized by SOC and preferred term. Subjects will be counted only once at the SOC level and will be counted once for each applicable preferred term; multiple occurrences of the same preferred term for a subject will be counted only once. SOCs, and preferred terms within SOC, will be displayed alphabetically. Similarly, AEs leading to discontinuation from the study will be presented by SOC and preferred term as well. The treatment-related AEs, defined as AEs with relationship of ‘Possibly’ or ‘Probably’ related to the study treatment, will be summarized by SOC and preferred term.

Summaries by SOC and preferred term and maximum intensity or relationship to study treatment will also be provided for AEs. A summary by SOC and preferred term and maximum intensity will be provided for treatment-related AEs as well. Subjects with multiple occurrences of the same SOC or preferred term will be summarized at the maximum intensity or the strongest relationship to study treatment reported for that adverse event. If a subject has an AE with unknown intensity, then the subject will be counted in the intensity category of “Severe”. If a subject has an AE with unknown relationship to study treatment, then the subject will be counted in the relationship category of “Related” even if the subject has another occurrence of the same event with a relationship to study treatment.

Additionally, the number and percentage of subjects experiencing AEs will be summarized by preferred term in an order of decreasing frequency.

The number and percentage of subjects experiencing serious AEs will be summarized by SOC and preferred term.

An overall summary table of the adverse events will be produced. This table displays the number and percentage of subjects who:

- have any treatment emergent adverse events
- have any treatment emergent adverse events at least possibly related to the study drug

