## 12.6 Clinical Laboratory Parameters

Shift analysis (High/Normal/Low), compared to the baseline result, at each visit and an overall view regardless of post-administration assessment time point, and descriptive statistics for the central laboratory values and changes from baseline at each visit will be presented by treatment group, for laboratory parameters collected in the study that include:

Hematology: Hematocrit, Hemoglobin, WBC with differential, RBC, Platelets

Blood Chemistry: Alanine transaminase (ALT), Albumin, Alkaline phosphatase (ALP), Aspartate aminotransferase (AST), Blood urea nitrogen (BUN), Calcium, Carbon dioxide, Chloride, total Cholesterol, HDL Cholesterol, LDL Cholesterol, Creatinine, Direct bilirubin, Glucose, Lactate dehydrogenase (LDH), Potassium, Sodium, total Bilirubin, total Protein, Triglycerides

Coagulation Factors: Protein C-activity and antigen, Protein S-activity, Protein S-antigen, Antithrombin III antigen, and Activated protein C resistance (APCR)

Endocrine: Glycated hemoglobin (HbA1C)

Hormones: Follicle stimulating hormone (FSH), Luteinizing hormone (LH), and Sex hormone-binding globulin (SHBG)

Urinalysis: Appearance, Color, Glucose, Ketones, Microscopic, Nitrites, Occult blood, pH, Protein, Specific Gravity

Biomarkers:

- Bone: C-telopeptide crosslink of type 1 collagen (CTX) – a marker of bone resorption; Alkaline Phosphatase, Bone Specific (BSAP) – a marker of bone formation
- Prostate: Prostate specific antigen (PSA)

Pharmacokinetic: Estradiol, Estrone (no shift analysis will be performed for Estradiol and Estrone data).

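### SAP 12.5 reports adverse events only as crude percentages, although stopping on testosterone is expected to lengthen observation as dose rises

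*SAP*

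**What the plan says.** SAP 12.5 (Adverse Events) states: "The number and percentage of subjects experiencing AEs will be summarized by SOC and preferred term". The other tables in that section (related, serious and fatal events, discontinuations, maximum intensity) have the same form: each subject counted once, as a number and a percentage. None uses patient-time, time to first event or a common window.

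How long a patient is observed depends on his T result. Protocol 4.3 gives as a reason to end participation: "The patient is no longer chemically castrated, after 4 weeks of double-blind treatment or anytime thereafter", shown by T of 50 ng/dL or more. A PSA rise is another reason. Protocol 9.1 says of AE collection: "The reporting period begins with the first dose of Study Drug (Study Day 1) and ends at Week 54 or the End of Study". SAP 4.1 puts the final visit 2 weeks after the last dose. SAP 4.3 gives the planning response rates: 5% placebo, 50% low, 80% mid, 95% high.

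The shift tables for vital signs, ECG and physical examination (SAP 12.2 to 12.4) are also shown "in an overall view regardless of post-administration assessment time point". SAP 12.6 plans "an overall view regardless of post-administration assessment time point" for laboratory values.

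Three planned outputs bear on the imbalance. SAP 8 tabulates non-completion by reason, SAP 12.1 tabulates applications and gel weight by dose group, and SAP 7 lists all data. SAP 2 and 4.3 record that the study was stopped at 34 patients, and SAP 11 drops inferential efficacy analyses. The text of SAP 5.2 was not available to check.

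**The concern.** Crude percentages compare arms fairly only when the arms are watched for similar lengths of time, or when events come early in every arm. Here the rule that ends observation is tied to the efficacy outcome, and the plan expects that outcome to differ widely by dose. Most placebo patients would be expected to leave by about Week 12. Most high-dose patients could stay to Week 24 or, by choice, to Week 52. For an event that accrues over time, equal hazards would then look like a dose response.

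Safety against placebo is part of the primary objective (SAP 3.1), and dose selection is the secondary objective (SAP 3.2). With inferential efficacy analyses dropped, descriptive tables are what remains for comparing doses. The overall shift tables raise a related point: a patient who stays longer has more scheduled visits at which to show an abnormal value.

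**Working it through.** **The plan's own figure.** SAP 4.3 claims at least 90% power with 30 per group (two-sided Fisher exact test, 5%). Exact enumeration gives 98.2% for low dose and over 99.99% for mid and high dose against placebo. The claim holds, and the planning rates are taken as stated.

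**Inputs from the documents.** Response p = 0.05, 0.50, 0.80, 0.95 (SAP 4.3). T visits every 2 weeks, with stopping from Week 4 (Protocol 3.0, 4.3). Final visit 2 weeks after the last dose (SAP 4.1). Maximum 52 weeks, with the part after Week 24 optional (SAP 4.1, Protocol 7.14).

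**Assumptions.** The documents do not give failure timing, extension uptake or AE rates. Failures are taken as even over Weeks 4, 6, 8, 10 and 12, with no other exits. Responders stop at horizon H.

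**Mean AE observation in weeks:** L = (1 − p) × mean(t + 2) + p × (H + 2), where mean(t + 2) = (6 + 8 + 10 + 12 + 14)/5 = 10. For H = 24, placebo is 0.95 × 10 + 0.05 × 26 = 10.8 and high is 0.05 × 10 + 0.95 × 26 = 25.2.

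| H | Placebo | Low | Mid | High | High/placebo | If all fail at Week 12 | If all fail at Week 4 |
|---|---|---|---|---|---|---|---|
| 12 | 10.2 | 12.0 | 13.2 | 13.8 | 1.35 | 1.00 | 2.1 |
| 24 | 10.8 | 18.0 | 22.8 | 25.2 | 2.33 | 1.74 | 3.6 |
| 52 | 12.2 | 32.0 | 45.2 | 51.8 | 4.25 | 3.25 | 6.1 |

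If half of the responders finish the extension and half stop at Week 24, the ratio is 38.5/11.5 = 3.3.

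**Sensitivity of the ratio (H = 12 / 24 / 52).**
- A 1-week wait for the central laboratory result before stopping makes the failure mean 11: 1.24 / 2.15 / 3.94.
- 20% of responders in every arm leave evenly at Weeks 4, 8 and 12: 1.28 / 2.08 / 3.69.
- 20% of Week 12 responders fail T at later visits: 2.26 / 3.98 for H = 24 / 52.
- The same 20% early exit, in high-dose responders only: for H = 24, high is 0.05 × 10 + 0.95 × (0.8 × 26 + 0.2 × 10) = 22.16, and 22.16/10.8 = 2.05.

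**Crude percentage at an equal hazard.** With an assumed 0.5 events per patient-year in every arm, crude = (1 − p) × mean[1 − exp(−0.5(t + 2)/52)] + p × [1 − exp(−0.5(H + 2)/52)]. Patients are per arm at 34/4 = 8.5.

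| H | Placebo | High | Patients, placebo vs high |
|---|---|---|---|
| 12 | 9% | 12% | 0.8 vs 1.1 |
| 24 | 10% | 21% | 0.8 vs 1.8 |
| 52 | 11% | 39% | 0.9 vs 3.3 |

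**Overall shift tables.** Scheduled post-baseline vital-sign visits, counting the final one, number 3, 4, 5, 6 or 7 for failure at Weeks 4 to 12 (mean 5), and 7, 13 or 20 for responders at H = 12, 24, 52. Placebo vs high is 5.1 vs 6.9, 5.4 vs 12.6 and 5.75 vs 19.25.

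**A caution on rates.** Suppose 20% in both arms have an event around Week 2. The rate is 0.2/(0.2 × 2 + 0.8 × L). For H = 24 this is 2.2 (placebo) vs 1.0 (high) per 100 patient-weeks, which favours high dose although incidence is equal.

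**The case against.** **The imbalance will be visible.** Disposition by reason, applications by dose group and full listings show differential stopping. This stands, and a careful reader could partly correct by hand. But none of these tables relates AEs to time, and applications omit the 2 post-dose weeks.

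**The magnitudes lean high.** They apply rates chosen to power 120 patients to a terminated study of 34. The Week 52 row needs every responder to consent to the extension and none to be cut short. This stands, so the figures are illustrations. At H = 12 the ratio falls to 1.0 if every failure comes at Week 12.

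**The practical effect may be small.** In the Week 12 case it is 0.8 vs 1.1 patients. No AE test is planned, and no dose-selection rule in the documents uses AE percentages. This limits the point to fairer description.

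**Stronger readings that the documents do not support.**
- A reader might infer that PSA stopping also lengthens observation with dose. No document gives PSA exit rates by dose; the gradient is documented for T only.
- A reader might infer that the tables conceal high-dose harm. For events that accrue over time, the bias overstates it.
- A reader might infer that every overall shift table gives high dose more looks. The only scheduled post-baseline physical examination is at early termination or end of study, so its timing differs, not its number. Coagulation factors, HbA1c, FSH/LH/SHBG and bone markers are first due at Week 12 and not at the final visit (Protocol Appendix 1). A patient who fails earlier has no scheduled post-baseline value at all.
- A reader might infer that by-visit tables hide the shrinking sample. SAP 7 already requires tables to show the number of subjects they rest on.

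**Conclusion.** The point holds as a cheap improvement, not as an error in the plan. The AE tables in SAP 12.5 carry no time dimension, while the T stopping rule and the planning rates together imply longer observation at higher dose. The direction is well supported. The size is not known: about 1.35, 2.3 and at most about 4.2 for the three horizons with failures even over Weeks 4 to 12, and 1.24, 2.15 and 3.94 with a 1-week laboratory lag. These figures rest on the planning response rates, the assumed failure timing and the absence of other exits. Early termination may narrow the gap. The bias concerns events that accrue over time; early-onset events are little affected. Confidence is medium, because realised exposure is not reported and SAP 5.2 could not be read.

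**What to change.** Keep the crude tables and add the following.

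- **SAP 12.1:** weeks of AE observation by arm, including the 2 post-dose weeks.
- **SAP 12.5**, by arm, for any, related and serious treatment-emergent AEs: a Kaplan-Meier time to first event or a Day 1 to Week 4 common-window table, together with patients with a first event per 100 patient-weeks at risk and an exact 95% CI. The rate should not stand alone, for the reason shown in the caution on rates. State that the Week 4 window cannot show later events, and that Kaplan-Meier assumes stopping is unrelated to AE risk within an arm.
- **SAP 12.2, 12.3 and 12.6:** footnote the overall vital-sign, ECG and routine laboratory shift tables with observation time by arm. For the 12.6 panels first due at Week 12 and not at the final visit, report instead the number per arm with any post-baseline value.

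No footnote is needed on by-visit tables or in SAP 12.4.

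The cost is a few descriptive tables from dates already collected, through a SAP revision or as additional exploratory analyses, which SAP 2 allows. The downside is imprecision. One event in 8.5 × 10.2 = 86.7 placebo patient-weeks is 1.15 per 100, with exact 95% CI 0.03 to 6.43.

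A separate matter, not needed to count patient-time from recorded dates, is that the stopping passages conflict and must be reconciled. SAP 4.1 and the Protocol synopsis give the T rule with no Week 4 condition (SAP 4.1: "he was no longer chemically castrated as demonstrated by testosterone levels greater than or equal to 50 ng/dL"), whereas Protocol 3.0 and 4.3 include one. For PSA, the study-design text of the Protocol synopsis has "a rise in PSA over baseline of ≥ 0.5 ng/mL is observed", as does SAP 4.1 in substance. Protocol 3.0 has "a rise over baseline PSA of > 0.5 ng/mL is observed", and Protocol 1.0, 4.3 and the synopsis entry on treatment duration also use a strict inequality.
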